8.1 Data Collection Tools and Source Document Identification

Source data will be collected and recorded in the trial participants files/medical records. They will be kept on a secured location at all times. The collection and processing of source data (from subjects enrolled in this trial) will be limited to those data that are necessary to fulfill the objectives of the trial. These data

must be collected and processed with adequate precautions to ensure confidentiality and compliance with applicable data privacy protection laws and regulations. Appropriate technical and organizational measures to protect the data against unauthorized disclosures or access, accidental or unlawful destruction, or accidental loss or alteration must be put in place. Personnel whose responsibilities require access to personal data agree to keep the data confidential.

Documentation of source data is necessary for the evaluation and validation of clinical findings, observations and other activities during a clinical trial. Source documentation serves to substantiate the integrity of trial data, confirms observations that are recorded and confirms the existence of trial participants. Furthermore source documentation must be available for the following to confirm data collected in the (e)CRF: subject identification, eligibility, and trial identification; trial discussion and date of informed consent; dates of visits; results of safety and efficacy parameters as required by the protocol; record of all adverse events and follow-up of adverse events; concomitant medication; drug receipt/dispensing/return records; trial drug administration information; and date of trial completion and reason for early discontinuation of trial drug or withdrawal from the trial, if applicable.

Data collection is the responsibility of the clinical trial staff at the site under the supervision of the investigator. The investigator will maintain complete and accurate documentation for the trial. All source documents will be reviewed by the clinical team to ensure that they are accurate and complete.

As defined in section 1.52 of the ICH Guideline for Good Clinical Practice (latest version of ICH E6) source documents may include: original documents, data and records (e.g. hospital records, clinical and office charts, laboratory notes....)

Case report forms

CRFs are provided for each subject in electronic/paper format. The trial data will be transcribed on a regular basis by trial personnel from the source documents onto an (e)CRF in a pseudonymised manner, and transmitted in a secure manner to the PI within the timeframe agreed upon between PI and the sites. The file will be considered to be the (e)CRF.

Worksheets may be used for the capture of some data to facilitate completion of the (e)CRF. Any such worksheets (including but not limited to copies of the (e)CRF) will become part of the trial participant's source documentation. All data relating to the trial must be recorded in (e)CRFs prepared by the investigator. Data must be entered into (e)CRFs in English. Designated site personnel must complete the (e)CRF as soon as possible after a subject visit, and the forms should be available for review at the next scheduled monitoring visit.

All subjective measurements (e.g., dairies, questionnaires, or ...) will be completed by the same individual who made the initial baseline determinations whenever possible. The investigator will ensure that data are recorded on the (e)CRFs as specified in the trial protocol and in accordance with the instructions provided.

All (e)CRF entries, corrections, and alterations must be made by the investigator or other authorized trial-site personnel. Proper audit trails are available to demonstrate the validity of the trial data. A certified copy of the completed (e)CRFs will be archived at the trial site.

Data handling and record keeping

The Investigator and the Participating Site shall treat all information and data relating to the Trial disclosed to Participating Site and/or Investigator in this Trial as confidential and shall not disclose such information to any third parties or use such information for any purpose other than the performance of the Trial. The collection, processing and disclosure of personal data, such as patient health and medical information is subject to compliance with applicable personal data protection and the processing of personal data .

The investigator will maintain a certified copy of (e)CRFs and all source documents that support the data collected from each trial participant, as well as all trial documents as specified in ICH/GCP Section 8, Essential Documents for the Conduct of a Clinical Trial, and all trial documents as specified by the applicable regulatory requirement(s). A Certified copy as specified in addendum 1.63 in ICH/GCP is a copy (irrespective of the type of media used) of the original record that has been verified (i.e. by a dated signature or by generation through a validated process) to have the same information, including data that describe the context, content and structure, as the original. The investigator will take measures to prevent accidental or premature destruction of these documents.

If data need to be transferred, this will be performed via a secured method of transfer taking into account all applicable security arrangements and regulations (such as the Belgian Privacy Act of 8 December 1992 on the protection of privacy in relation to the processing of personal data and the European Data Protection Act). Receiving party will agree to keep the transferred data confidential at all times.

8.2 Access to Data, Monitoring, Audit and Inspection

The investigator will permit trial-related monitoring, audits, EC review and regulatory inspection, providing direct access to all related source data / documents.

(e)CRFs and all source documents, including progress notes and copies of laboratory and medical test results must be available at all times for review by the sponsor's clinical trial monitor, auditor and inspection by health authorities. The accuracy of the data will be verified by review of the source documents.

8.3 Archiving

As specified in ICH/GCP Section 8.1 Addendum the sponsor and investigator/institution should maintain a record of the location(s) of their respective essential documents including source documents. The storage system used during the trial and for archiving (irrespective of the media used) should provide for document identification, version history, search and retrieval.

Essential documents for the trial should be supplemented or may be reduced where justified (in advance of trial initiation) based on the importance and relevance of the specific documents to the trial.

The sponsor should ensure that the investigator has control of and continuous access to the CRF data reported to the sponsor. The sponsor should not have exclusive control of those data. When a copy is used to replace an original document (e.g. source documents, CRF), the copy should fulfill the requirements for certified copies. The investigator/institution should have control of all essential documents and records generated by the investigator/institution before, during and after the trial.

The Sponsor is responsible for archiving trial specific documentation (such as but not limited to protocol, potential amendments, copy of (e)CRF burned on CD, final report and database) for at least twenty years. Site-specific trial documents (such as but not limited to ICF) will be archived locally on site according to local practice and guidelines. Archived data may be held on electronic record, provided that a back-up exists and that hard copies can be obtained, if required. Destruction of essential documents will require authorisation from the Sponsor.

9 Ethical and Regulatory Considerations

9.1 Ethics Committee (EC) review & reports

The trial will be conducted in compliance with the principles of the Declaration of Helsinki (most recent version), the principles of GCP and in accordance with all applicable regulatory requirements. Before the start of the trial, this protocol, the informed consent forms and other related documents e.g. advertisements and general practitioners information letters, will be submitted for review to the EC and to the Federal Agency for medicines and health products (FAMHP) for Clinical Authorization (the below mentioned obligations shall only apply to the extent applicable). The trial shall not commence until such approvals have been obtained.

Any subsequent protocol amendments will be submitted to the EC and Regulatory Authorities for approval. No substantial amendment that require review by EC will be implemented until the EC grants a favorable opinion for the trial. The CI acknowledges that amendments may also need to be reviewed and accepted by the FAMHP before they can be implemented in practice at sites.

The trial can and will be conducted only on the basis of prior informed consent by the trial participants, or their legal representatives, to participate in the trial. Extensive discussion of risks and possible benefits of participation will be provided to the patients and/or their families. The participating site shall obtain a signed informed consent form for all trial participants prior to their enrollment and participation in the trial in compliance with all applicable laws, regulations and the approval of the (local) Ethics Committee, if required. The participating site shall retain such ICFs in accordance with the requirements of all applicable regulatory agencies and laws. All correspondence with the EC/FAMHP shall be retained in the Trial Master File/Investigator Site File.

The CI acknowledges that it is his responsibility to produce annual progress reports (APR) and he will do so by submitting to the EC/FAMHP within 30 days of the anniversary date on which the favorable opinion was given, and annually until the trial is declared ended.

The PI shall notify the EC/FAMHP of the end of the Trial. Should the trial be ended prematurely, the PI will notify the EC/FAMHP and include the reasons for the premature termination. The PI will submit a final report with the results, including any publications/abstracts, to the EC/FAMHP.

9.2 Peer review

This trial protocol was peer reviewed by certain independent experts. Peer review was conducted by expert referees to the professional and scientific standards expected for clinical studies.

9.3 Regulatory Compliance

Before the start of the trial, this protocol and other related documents will be submitted for review to the Federal Agency for medicinal products for Clinical Trial Authorisation (FAMHP). The trial shall not commence until such approvals have been obtained.

This trial protocol and the conduct of the trial in general is in compliance with applicable law, including but not limited to the Belgian law of May 7th 2004 regarding experiments on the human person and any relevant amendments.

9.4 Protocol/GCP compliance

The CI is responsible for ensuring that the clinical trial is performed in accordance with the protocol, current ICH guidelines on GCP, and applicable regulatory and country-specific requirements. GCP is an international ethical and scientific quality standard for designing, conducting, recording, and reporting studies that involve the participation of human subjects. Compliance with this standard provides public assurance that the rights, safety, and well-being of trial participants are protected, consistent with the principles that originated in the Declaration of Helsinki, and that the clinical trial data are credible.

It is acknowledged and agreed that prospective, planned deviations or waivers to the protocol are not allowed under applicable regulations on clinical studies and must not be used. However, should there be an accidental protocol deviation, such deviation shall be adequately documented on the source documents and on the relevant forms and reported to the Chief Investigator and Sponsor immediately. Protocol deviations which are found to frequently recur, will require immediate action. CI acknowledges that such recurring protocol breaches could be potentially classified as a serious violation.

It is understood that “a serious violation” is likely to effect to a significant degree

- the safety or physical or mental integrity of the participants of the trial; or
- the scientific value of the trial

9.5 Data protection and patient confidentiality

The trial will be conducted in compliance with the requirements of the Belgian Privacy Act of 8 December 1992 on the protection of privacy in relation to the processing of personal data and the European Data Protection Act. Any collection, processing and disclosure of personal data, such as patient health and medical information is subject to compliance with the aforementioned personal data protection laws.

Any personal data shall be treated as confidential at all times including during collection, handling and use, and that the personal data (including in any electronic format) shall be stored securely at all times and with all technical and organizational security measures that would be necessary for compliance with data protection legislation. The Sponsor shall take appropriate measures to ensure the security of all personal data and guard against unauthorized access thereto or disclosure thereof or loss or destruction while in its custody.

The personal data of trial participants will be encoded, which means that they can only be related to an identifiable person by means of a unique code. The unique code will only be in the possession of the members of the trial team who are in direct contact with the trial participants. In no event will the coded personal data include personal identifiers, including any Trial participant's initials. Such coded personal data can only be traced or linked back by said trial team members, and said trial team members shall treat these codes as strictly confidential.

All trial related data and documents will be stored for at least twenty (20) years, in accordance with Belgian legislation.

9.6 Indemnity

The Sponsor shall throughout the duration of the trial effect and maintain with a reputable insurance company a policy or policies of insurance providing an adequate level of cover in respect of all risks which may be incurred by the Sponsor arising out of the Sponsor's performance of the trial, including the insurance that is required to be taken out as sponsor of the trial as set out in the Law of 2004.

In accordance with the Belgian Law relating to experiments on human persons dated May 7, 2004, Sponsor shall assume, even without fault, the responsibility of any damages incurred by a Trial Patient and linked directly or indirectly to the participation to the Trial, and shall provide compensation therefore through its insurance.

The terms or the amount of cover of any insurance shall not relieve the Sponsor of any liabilities under the clinical trial agreement.

9.7 Amendments

In accordance with the Belgian law of May 7th 2004 regarding experiments on the human person, the Sponsor may make a non-substantial amendment at any time during a trial. If the Sponsor wishes to make a substantial amendment to the clinical trial agreement or the documents that supported the original

application for the CTA, the Sponsor must submit a valid notice of amendment to the licencing authority (FAMHP; if applicable) for consideration. If the Sponsor wishes to make a substantial amendment to the EC application or the supporting documents, the Sponsor must submit a valid notice of amendment to the EC for consideration. The FAMHP and/or the EC will provide a response regarding the amendment within 28 days of receipt of the notice. It is the Sponsor's responsibility to decide whether an amendment is substantial or non-substantial for the purposes of submission to the FAMHP and/or EC (if applicable).

2. GENERAL BACKGROUND, OBJECTIVES AND AIMS

Fungal infections cause a serious threat to critically ill patients. The triazole antifungal drugs are the most important drugs for managing infections due to aspergillus moulds and the principal study (S60744) will investigate the role for those drugs in prophylaxis. Adequate treatment and prophylaxis of IAA is of the greatest essence but regrettably failure to therapy can occur. One of the shortcomings in previous studies is that pop-PK in critically ill patients haven't been investigated. As a consequence, solid recommendations of regimens other than the once investigated in hematology patients cannot be drawn based on previous models.

With this research we believe we can resolve multiple critical questions/objectives

- 1) Document pharmacokinetics of posaconazole in a cohort of critically ill patients on IV posaconazole to help determine the PK
- 2) Determine the impact of known and unknown covariates on posaconazole PK

The derived PK model can be used for modeling and simulation purposes to demonstrate target attainment in a wide distribution of patients.

As a general statement, we hypothesize that altered clearance is more likely in critically ill patients than altered clearance in hematology patients. We expect that a difference in clearance is largest in critically ill patients. Thus if we want to identify changes in PK of posaconazole, this is the cohort that is best used to address the question.

3. PATIENTS AND METHODS

3.1. Study characteristics

Open label, multiple dose, pharmacokinetic study on intravenous posaconazole.

3.2. Inclusion and exclusion criteria

Patients who are randomized in the posaconazole prophylaxis-group in the principal study (S60744) are automatically eligible for this PK study.

3.3. Study design

I) Posaconazole sampling

a. Group I: extensive sampling (UZ Leuven and Radboudumc)

- **Plasma**
 - A full PK curve will be taken on two extensive sampling days: day 2 and day 5. Intravenous administration of posaconazole sampling scheme: $t = 0$ (pre-dose), 1.5 (= end of infusion), 2, 3, 4, 6, 8, 10, 12, 18, and 24 hours post infusion (11 samples).
 - On non-PK days (until day 7), samples will be taken daily just prior to the daily infusion therapy. The exact times of sampling will be recorded in the case report forms.
 - In the full PK group a maximum of 30 PK plasma samples will be taken. The total volume associated with this setup is 60 ml. No problems for the patients are expected with this limited amount of blood taken. In previous studies similar setup was used and approved by the ethics committee.
 - Together with the posaconazole concentration, the concentration of the glucuronide metabolite will be reported (no extra sample).
- **BAL (bronchoalveolar lavage)** – only in patients with mechanical ventilation and when medically indicated
 - The BAL fluid and alveolar cells from the BAL carried out 48 hours after influenza diagnosis (see principal study (S60744)) will be analyzed to measure the posaconazole concentration. Bronchoscopy will only be performed if the safety of the patient will not be compromised.
 - If other BALs are carried out by the treating physician, a part of that BAL fluid and alveolar cells will be analyzed to measure the posaconazole concentration.
 - BAL sampling by mini broncho-alveolar lavage (2×20 mL NaCl 0.9%) and a plasma sample at the same time.
 - Urea is determined simultaneously on BAL fluid and in plasma to correct for the dilution with NaCl 0,9%.

b. Group II: limited sampling (other investigation sites)

- **Plasma**
 - A limited sampling strategy will be deployed taking samples on the same days (day 2 and 5) but at less frequent time points : between 1.5 – 3 hours ; between 4-8 hours ; between 8-12 hours and between 12-24 hours (4 samples in total).
 - On non-PK days (until day 7), samples will be taken daily just prior to the daily infusion therapy. The exact times of sampling will be recorded in the case report forms.

2) Other data:

- a. Data on critical illness, albumin, renal and liver function and albumin will be used for covariate analysis of posaconazole pharmacokinetics. One extra whole blood cell sampling tube will be used for genotyping (UGT1A4).
- b. The clinical response of the posaconazole prophylaxis will be evaluated in the principal study (S60744).

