b: On NS, BA or BAL within the last 7 days before ICU admission or within 2 days after ICU admission; or based on a positive rapid test if PCR not available

c: BAL GM, BAL culture and serum GM within 48h after influenza diagnosis to collect mycological evidence for IAA-infection

d: BAL GM, BAL culture and serum GM between day 2 after randomization and ICU discharge, at the discretion of the treating physician, or later during ICU admission in case of clinical respiratory deterioration

e: Provided by either (A) a positive culture of *Aspergillus* cultured from BAL, (B) ≥2 positive cultures of *Aspergillus* cultured from a sputum or a bronchial aspirate or (C) a galactomannan (GM) optical density of ≥1 in BAL or ≥0.5 in serum

f: Study drug related adverse events

I Background and Rationale

Invasive aspergillosis has been regarded as an infectious complication of specific immunocompromised patients, which affects a relatively small group of patients. However, in recent years aspergillus disease has become a prominent problem in ICU-patients.

Influenza-associated aspergillosis (IAA) was recently found to be a frequent and severe complication of influenza pneumonia in critically-ill patients.[1] A retrospective observational study during the 2015/2016 influenza season indicated that among 144 patients admitted to the ICUs of all eight Dutch University Medical Centres with influenza, 23 (16%) developed IAA.[2] The underlying diseases in these patients were diverse, and 7 patients had been previously healthy. A 61% mortality rate was observed, including 5 of 7 previously healthy patients who died.[2] It is thus clear that IAA is an early and frequent complication of severe influenza pneumonia, and that delay in diagnosis and treatment increases the probability of death in these critically ill patients. Early diagnosis is difficult due to unspecific clinical and radiological presentation. [1,2]

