2.4 Trial Design

This study is an interventional non-blinded randomized controlled multicenter study.

- Critically ill patients with PCR-confirmed influenza (for details: see inclusion criteria) are eligible for inclusion in this study and will be randomized to or the posaconazole prophylaxis group or the SOC group. Within 48 hours after influenza diagnosis with a bronchoscopy with BAL (minimum volume of 2x20mL, 0.9% NaCl) and a with a serum galactomannan will be performed as part of routine ICU care in this type of patients. As any bronchoscopy, this bronchoscopy will only be performed if the safety of the patient will not be compromised. If an IAA-infection is suspected based on the result of this BAL ((A) *Aspergillus* cultured from BAL, or (B) a galactomannan (GM) ≥ 1 in BAL or ≥ 0.5 in serum), the patient will be withdrawn from the study and antifungal treatment will be started. The type and duration of antifungal therapy will be at the discretion of the treating physician.
- SOC further includes:
 - The treating physician can decide to perform an additional bronchoscopy with BAL between day 2 after randomisation and ICU discharge in case of respiratory deterioration and clinical suspicion of an IAA-infection. Any bronchoscopy will only be performed if the safety of the patient will not be compromised. In case of positive mycological evidence of an IAA-infection, a CT thorax without IV contrast is performed if possible. If an IAA-infection is documented, antifungal treatment will be started and - in case the IAA-infection is diagnosed before the ending of the study drug - the patient will be withdrawn from the study. Again, type and duration of antifungal therapy will be at the discretion of the treating physician.

- Oseltamivir (non-IMP) will be started at the discretion of the treating physician from the first day of ICU admission as 2*150 mg/day for a duration of 10 days. If oseltamivir had already been started up before ICU admission, oseltamivir treatment will be continued up to a total of 10 days.

*If *Aspergillus* is **only** cultured from sputum (and not from BAL) within the first 48 hours after the influenza diagnosis, the patient will not be withdrawn from the study

3 Trial Medication / Drug

Drug Name	IMP or non-IMP
Posaconazole	IMP

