3.1 Investigational Medicinal Product and Dosing Regimen

If a patient is randomized non-blinded to the **posaconazole prophylaxis** group, posaconazole (Noxafil, MSD) will be started intravenously from day 1 of randomization (2*300mg/d on day 1, followed by 1*300mg/d from day 2 for 7 days). Noxafil concentrate injections (vials made of type I glass containing 18mg posaconazole /mL, 300mg posaconazole/vial in total) for intravenous use will be provided by MSD. In both patient groups (prophylaxis and SOC) **oseltamivir** (non-IMP) will be started at the discretion of the treating from the first day of ICU admission as 2*150 mg/day for 10 days. If oseltamivir had already been started up before ICU admission, oseltamivir treatment will be continued up to a total of 10 days.

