4.1 Inclusion criteria

Patients eligible for inclusion in this trial have to meet **all** of the following criteria:

1. Written informed consent must be obtained from the patient or his/her legal representative prior to any study procedures
2. Adult patient (≥ 18 years)
3. PCR-confirmed influenza based on nasopharyngeal swab (NS), bronchial aspirate (BA) or broncho-alveolar lavage (BAL) within 7 days before ICU admission or within 48 hours after ICU admission.
If PCR is not available a positive result of a rapid test is required (a negative rapid test does not imply absence of influenza and thus requires confirmation by PCR)
4. Influenza symptoms present for no more than 10 days before ICU admission
5. Respiratory distress as the main reason for ICU admission. Respiratory distress will be defined as tachypnea with an respiratory rate ≥ 25 x/min and a $\text{paO}_2/\text{FiO}_2$ -ratio ≤ 300 with or without (bilateral) infiltrates.

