5.5.2 Treatment Visits

Day 1 = day of randomization:

- Bronchoscopy with BAL sampling, serum galactomannan (SOC)
- Pregnancy screening negative
- Start study medication
- Gather baseline clinical data including demographic, biochemical, microbiological and radiological data (SOC)

Day 2 – ICU discharge:

- Withdrawal of patients from study if mycological evidence of IAA-infection on BAL of day 1
- Continuation of study medication up to day 7
- Gather clinical data including demographic, biochemical, microbiological and radiological data (SOC)
- Assess presence of IAA-infection (SOC)
- Assess outcome parameters: ICU mortality, IAA-infection (SOC)

30 days after randomization:

Assess outcome parameters: hospital and/or 30-day mortality and a retrospective assessment of IAA-infection (SOC)

90 days after randomization:

- Assess outcome parameters: hospital and/or 90-day mortality and a retrospective assessment of IAA-infection (SOC)

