7.2 Data Analysis

Appropriate statistical tools will be used to test for significance with respect to the primary and secondary endpoints.

Categorical variables will be reported as a percentage and continuous variables as mean \pm standard deviation (SD) or median and interquartile range (IQR), as appropriate. Differences in categorical variables will be assessed using the Chi squared test or the Fischer's Exact test and for the analysis of continuous variables the Student's t test or the Mann-Whitney U test will be used, where appropriate. P values <0.05 are considered significant. Patients that die during the trial duration will also be included in the statistical analysis.

The primary endpoint analysis will consist of a one-sided fisher-exact test in which the proportion of cases of IAA will be compared between both groups. The population included in this analysis will consist of a modified intent to treat population. This MITT population consists of all patients that received at least 1 posaco/placebo administration but excluding the patients in which a diagnosis of IAA was made on the basis of the BAL sample taken on day 1 because these patients in fact had an IAA at the day of inclusion.

8 Data handling

Patient data will be encoded: which means that personal data can only be related to an identified or identifiable person by means of a code.

Demographic, biochemical, microbiological and radiological data will be collected prospectively as a part of clinical routine. Samples will be obtained for characterization of the influenza type and for *Aspergillus* diagnosis including culture, galactomannan and PCR. These samples are part of daily routine, no additional samples for this study will be taken. All *Aspergillus* colonies will be screened for azole resistance, using an agar-based selection tool, and relevant samples, i.e. BAL fluid, will be stored for direct detection of resistance mutations by PCR. Clinical *A. fumigatus* isolates will be sent the National Mycology Reference Laboratory in Leuven (Belgium) or Nijmegen (the Netherlands) for MIC-testing and analysis of azole-resistance mutations. A blinded data review committee following a pre-defined case definition will classify patients with evidence for primary and breakthrough IAA-infection.

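### The MITT exclusion for IAA present at inclusion rests on a BAL that no passage places before allocation or first dose, so exclusion can differ by arm

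*Combined protocol and SAP*

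**What the plan says.** Five places deal with the early BAL.

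- **Section 2.4** times it from diagnosis: "Within 48 hours after influenza diagnosis with a bronchoscopy with BAL". A positive culture or galactomannan leads to withdrawal from the study. The bronchoscopy is done only when it is judged safe.
- **Flowchart footnote c**, attached to the randomisation (day 1) column, uses the same anchor: "BAL GM, BAL culture and serum GM within 48h after influenza diagnosis to collect mycological evidence for IAA-infection".
- **Section 5.5.2** ties the action to a study day: "Withdrawal of patients from study if mycological evidence of IAA-infection on BAL of day 1".
- **Section 7.2** defines the primary analysis set as patients with at least one administration, "excluding the patients in which a diagnosis of IAA was made on the basis of the BAL sample taken on day 1". Its stated reason is that these patients already had IAA when they were included.
- **PK appendix, 3.3**, takes "The BAL fluid and alveolar cells from the BAL carried out 48 hours after influenza diagnosis", refers back to the principal study for that BAL, and says that it "will be analyzed to measure the posaconazole concentration. Bronchoscopy will only be performed if the safety of the patient will not be compromised".

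On dosing, section 3.1 says that "posaconazole (Noxafil, MSD) will be started intravenously from day 1 of randomization". Day 1 is therefore the day of randomisation and of the first dose. The comparator is standard of care, and the trial is not blinded.

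**The concern.** Removing randomised patients from the primary analysis is defensible when the reason is a baseline fact that neither treatment nor knowledge of the arm can influence. Infection already present at inclusion is such a fact only if the test for it is taken before the arm is known.

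Here the sample may be taken after allocation, and in one arm after a mould-active drug. Two things can then differ between arms: whether the bronchoscopy is done, since the safety judgement can be made with the arm known, and what the sample shows. A patient infected at inclusion could be excluded from the SOC arm while a similar patient stays in the posaconazole arm. That patient later becomes either an apparent prophylaxis failure or an undetected non-case. The planning rates imply only about 12.5 and 2.5 cases in 50 patients per arm (25% and 5% of 50), so a few such classifications matter.

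**Working it through.** **1. Order of sampling, allocation and dose.**

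| Place | Anchor for the BAL | Order relative to allocation or first dose |
|---|---|---|
| 2.4, footnote c | within 48 h of influenza diagnosis | not stated |
| 5.5.2, 7.2 | day 1 | not stated |
| PK 3.3 | 48 h after diagnosis | posaconazole assayed, so drug expected in some samples |

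Section 5.5.2 lists the BAL above the start of study medication, but it lists the gathering of baseline data below it. The list is therefore not a sequence.

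**2. A gap between the withdrawal rule and the exclusion rule.** Suppose influenza is diagnosed on the day of randomisation. The 48 h window then runs to about day 3. A positive BAL on day 2 or 3 is an early withdrawal under 2.4 but not an MITT exclusion under 7.2, which covers day 1 only. It could count as a primary event. In addition, 2.4 lets serum galactomannan trigger withdrawal, while 7.2 names only the BAL.

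**3. The plan's own sample size.** Inputs from 7.1 and 7.2: 25% versus 5%, one-sided 0.05, power 80%.

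- Uncorrected: n₀ = [1.645·√(2·0.15·0.85) + 0.842·√(0.25·0.75 + 0.05·0.95)]² / 0.20² = 38.4, so 39 per arm.
- Continuity-corrected: n = (n₀/4)·[1 + √(1 + 4/(n₀·0.20))]² = 47.8, so 48 per arm, against the stated 47.
- Exact power of the planned one-sided Fisher test: 82.7% at 47 per arm, 85.3% at 50 per arm.

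**4. Illustration of size.** Section 7.1 randomises 110 to keep 100, which leaves 10 spare, or 5 per arm. The following are assumptions, not in the documents: all 5 are baseline IAA; a share s of posaconazole-arm BALs is on drug; a share m of cases sampled on drug is missed. The number retained in the posaconazole arm only is k = 5·s·m. Power and type I error are exact, with 50 per arm.

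*Missed cases later counted as IAA.* Posaconazole rate = (2.5 + k)/(50 + k); SOC 25%.

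| s | m | k | Posaconazole rate | Power |
|---|---|---|---|---|
| – | 0 | 0 | 5.0% | 85.3% |
| 100% | 10% | 0.5 | 5.9% | 80.1% |
| 100% | 30% | 1.5 | 7.8% | 68.7% |
| 100% | 50% | 2.5 | 9.5% | 57.0% |
| 30% | 10% | 0.15 | 5.3% | 83.8% |
| 30% | 30% | 0.45 | 5.8% | 80.6% |
| 30% | 50% | 0.75 | 6.4% | 77.3% |

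*Missed cases never detected, no true effect.* With s = 100%, the posaconazole rate is 12.5/(50 + k) = 24.8%, 24.3% or 23.8%. One-sided type I error is 3.1%, 3.5% or 4.0%, against 2.9% when none is missed. Passing 5% takes harsher assumptions: with 55 randomised per arm, 10% baseline IAA and every posaconazole-arm case missed, it is 6.0%.

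**The case against.** The strongest reply is that 7.2 is narrower than 2.4. It excludes only on a day-1 BAL, so exposure to drug before the sample that decides exclusion is at most part of one day. That stands, and it limits the likely effect. It does not supply an order within day 1, and it creates the gap for positives on day 2 or 3.

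A reader might infer that the passages contradict each other outright. They need not. A BAL on day 1, after the first dose and within 48 h of diagnosis, fits them all if the PK wording is read as shorthand for the window in 2.4. The defect is an unstated order and two unaligned anchors.

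A reader might also infer that the window fails before ICU admission, because 4.1 accepts influenza confirmed "within 7 days before ICU admission or within 48 hours after ICU admission". Taken literally, the window could close five days before admission (−7 days + 48 h) or run to 96 h after it (48 h + 48 h). But 2.4 describes this BAL as routine ICU care, exclusion criterion 5 removes transferred patients with mycological evidence, and the 96 h end does not describe the MITT rule. No consequence for the analysis follows.

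The PK assay covers only ventilated patients with a medical indication at two sites. It shows that some samples are expected on drug, not that all are.

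Finally, a blinded committee classifies primary and breakthrough IAA. This helps with classification but cannot recover a sample that was never taken or was falsely negative.

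**Conclusion.** The point holds as a gap in the definition of the primary analysis set. An exclusion justified as a baseline fact is allowed to depend on a sample taken after allocation, and in one arm after drug. The missing order is clear from the text; the effect is not.

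The size is unknown, and so is the direction. It depends on how many baseline cases there are, how many are sampled on drug, how many are then missed, and whether those surface later. Missed cases that surface later cost power; those that never surface favour posaconazole. The lowest power figures require that all spare patients are baseline IAA, although 7.1 gives no reason for the ten extra and the MITT set also requires an administration. They require too that every posaconazole-arm BAL is on drug and that every missed case later counts. They are a worst-case illustration. A reader who took them as an estimate of bias, or concluded that the primary result must be biased, would go further than the documents allow.

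**What to change.** - **7.2:** let only samples collected before randomisation trigger the baseline exclusion, by the same rule in both arms. Keep patients with no such sample, including those in whom bronchoscopy was not safe, in the MITT set. State whether serum galactomannan counts toward the exclusion.
- **2.4, footnote c, 5.5.2, 7.2 and PK 3.3:** reconcile these to one anchor for the baseline sample, collected before allocation is released where feasible. Results need not be known at randomisation. State how positives on day 2 or 3 are treated in the analysis.
- **CRF:** record date and time of BAL, randomisation and first dose.
- **Analysis:** report all randomised patients as a sensitivity analysis.

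The posaconazole assay in the PK appendix can stay. Measuring drug biases nothing, and the levels would help show which BALs were taken on drug.

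The cost is wording in five places, three time fields and one further analysis; no procedure is added. There are two downsides. Allocation may wait briefly for a bronchoscopy, and some patients infected at baseline but sampled late will stay in the MITT set, though under the same rule in both arms.
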